4.9 Additional Analyses

4.9.1 Immunogenicity Analysis

1. The results of the anti-MOR00208 antibody assessment will be listed for each anti-MOR00208 sample analyzed. The analysis will be performed using the IAS.

Note: For 2. and 3. below, “negative” is defined as a sample reported negative in the screening assay OR confirmatory assay. “Positive” is defined as a sample being reported positive in the confirmatory assay.

Furthermore, the absolute number and percentage of the following categories will be tabulated by visit:

2. Patient has positive anti-MOR00208 antibodies (yes/no/missing):
 - yes, if a titer is available
 - no, if result is reported as negative
 - missing, if anti-MOR00208 measurement is not available

3. In addition, the absolute number and percentage of patients who develop anti-MOR00208 antibodies will be tabulated using the following categories:
 - yes, if the patient has at least one positive post-baseline sample containing anti-MOR00208 antibodies, baseline sample has to be tested negative
 - no, if baseline as well as all post-baseline results are negative
 - not evaluable, if the baseline sample of the respective patient was tested positive
 - missing, if no post-baseline anti-MOR00208 measurement is available
4. Results (n, mean, StD, median, minimum, maximum) of semi-quantitative anti-MOR00208 antibody titer determinations of confirmed positive samples assessments will be tabulated by visit.

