4.5.2 Clinical Experience with MOR00208 in CLL

Protocol XmAb5574-01:

A Phase 1 Study of XmAb[®]5574 to Evaluate the Safety, Tolerability, and Pharmacokinetics in Patients with Relapsed or Refractory Chronic Lymphocytic Leukemia

The first study in humans was a phase I trial exploring the use of MOR00208 (also known as XmAb[®]5574 or MOR208) in adult patients diagnosed according to International Workshop on CLL guidelines (Hallek et al., 2008) with active, treatment-requiring R/R CLL/SLL. Results of the study were reported by Woyach et al. (2014a).

Twenty-seven patients were enrolled to 6 escalating dose levels, with expansion at the highest dose level of 12 mg/kg. Nine doses of MOR00208 were infused over 8 weeks. The maximum tolerated dose (MTD) was not reached; the drug was generally well tolerated, IRRs of grade 1 or 2 being the most common toxicities. Treatment-related grade 3 or 4 AEs occurred in 5 patients and included neutropenia, thrombocytopenia, increased aspartate aminotransferase (AST), febrile neutropenia, and tumor lysis syndrome (TLS). MOR00208 showed preliminary efficacy, with 18 patients (66.7%) responding by physical examination criteria and laboratory studies, and 8 patients (29.6%) responding by computed tomography (CT) criteria. MOR00208 showed a terminal elimination half-life of approximately 14 days. A dose of 12 mg/kg was recommended for use in subsequent studies.

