3.1 Study Objectives and Endpoints

Objectives and endpoints are identical for both cohorts with one exception regarding the definition of the overall response rate. Details are specified in **Table 1**.

Table 1: Overview of Study Objectives and Endpoints

Study objective	Endpoint	Analysis

Primary objective:
 
 To determine the safety of MOR00208 combined with idelalisib or venetoclax 	
Primary endpoint:
 
 Incidence, frequency and severity of adverse events (AEs) 	See section 4.10.1

Secondary objectives:
 
 To determine the quality of the response To assess the potential immunogenicity of MOR00208 (anti-MOR00208 antibody formation) To assess the pharmacokinetic (PK) profile of MOR00208 	
Secondary endpoints:
 
 Best objective response rate (ORR): 
 Definition for Cohort A: percentage of patients achieving a complete response (CR), a partial response (PR) or a partial response with lymphocytosis (PRL). Definition for Cohort B: percentage of patients achieving a CR or a PR. Anti-MOR00208 antibody formation (ADA): number and percentage of patients who develop anti-MOR00208 antibodies; Titer determination; Characterization of ADA-positive samples (neutralizing vs non-neutralizing). Pharmacokinetic analysis for MOR00208: plasma concentration-time profiles of MOR00208 and appropriate individual PK parameters (e.g., accumulation ratios). 	
See section 4.8.1
 
See section 4.9.1
 
See section 4.9.2

[figure not shown]

Exploratory objectives:
 
 • To assess minimal residual disease (MRD) in patients achieving a complete or partial response • To explore putative predictive biomarkers 	
Exploratory endpoints:
 
 • Proportion of patients with MRD-negativity • Absolute and percentage change from baseline in measurements for B-, T- and natural killer (NK) cell populations 	
See section 4.9.3
 
See section 4.9.4

--	---	---

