⁹During Cycles 4 through 24, anti-MOR00208 antibody samples and MOR00208 PK samples (all to be collected pre-dose only) will be collected in odd numbered cycles only (i.e., Cycles 5, 7, 9, 11, etc.)

¹⁰B/T/NK cell count only in Cycle 4 of additional treatment period.

¹¹**For patients with CR:** a MRD assessment from bone marrow aspirate and a local analysis of bone marrow aspiration/biopsy has to be performed for confirmation of CR at least 8 weeks after the CR criteria for tumor response are first met. The result of the CT scan need to be obtained first; if this does not confirm a CR, then a biopsy should not be performed.

For patients with PR and PB MRD negativity: an MRD assessment from bone marrow aspirate/peripheral blood has to be performed at least 8 weeks after the PB MRD negativity was detected.

¹²If positive for hepatitis B serology needs to be followed up locally every 2 months.

¹³Peripheral blood sample for MRD assessment has to be taken at C4D1, C7D1, C13D1, C19D1, etc. until BM MRD negativity was confirmed.

For CR patients only: An additional PB sample needs to be obtained at the time when CR is confirmed by CT.

¹⁴Patients with positive serology or with other evidence of a history of CMV infection at screening should be carefully monitored with PCR

(a) monthly, if initial PCR result has been negative without associated clinical signs of CMV infection or

(b) weekly, if significant CMV viremia has been detected.

¹⁵During ramp-up of venetoclax patients will receive 20 mg (C1D8), 50 mg (C1D15), 100 mg (C1D22), 200 mg (C2D1) and 400 mg (C2D8), if no contraindications

¹⁶**Cohort B** –Venetoclax+MOR00208 patients only.

¹⁷**Cohort A** – Idelalisib+MOR00208 patients only.

¹⁸In cases when an unscheduled visit needs to be performed during ramp-up phase of venetoclax (e.g., due to dosing interruption or reduction of venetoclax which leads to changed treatment schedule of venetoclax), no risk reassessment for TLS needs to be performed at respective regular visit(s) when MOR00208 is administered.

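### SAP 4.9.1 cannot count a boosted antibody response and cannot tell a true ADA negative from one possibly masked by drug, so treatment-emergent ADA may be understated

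*SAP*

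**What the plan says.** SAP 3.1 (Table 1) lists ADA formation as a secondary endpoint, expressed as the "number and percentage of patients who develop anti-MOR00208 antibodies". Protocol 12.7 leaves the details to the SAP, so SAP 4.9.1 is where the rules belong.

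- **Sample level.** A sample is negative when it "is defined as a sample reported negative in the screening assay OR confirmatory assay", and positive when the confirmatory assay is positive. Neither rule refers to drug in the sample.
- **Patient level (item 3).** Four categories are given: "yes, if the patient has at least one positive post-baseline sample containing anti-MOR00208 antibodies, baseline sample has to be tested negative"; *no*, which needs a negative baseline and only negative later results; "not evaluable, if the baseline sample of the respective patient was tested positive"; and *missing*, when there is no post-baseline result.
- **Titers (item 4).** Results "of semi-quantitative anti-MOR00208 antibody titer determinations of confirmed positive samples assessments will be tabulated by visit".
- **Sampling (SAP 3.4, Table 2).** ADA and MOR00208 concentration are both scheduled at C1D1, C2D1, C3D1 and the end-of-treatment (EOT) visit. In Cycles 4 to 24, "anti-MOR00208 antibody samples and MOR00208 PK samples (all to be collected pre-dose only) will be collected in odd numbered cycles only". EOT falls preferably within 30 days of the last study treatment. No ADA sample is scheduled later. The sub-study (Protocol Appendix M, Table 15) measures MOR00208 for about six months after its first visit but takes no ADA sample.

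**The concern.** Two rules bear on the count. First, a patient with antibodies before treatment whose titer climbs on treatment has had an immune response to the drug, but item 3 offers no path from *not evaluable* to *yes*. The titers needed to see the rise are determined anyway.

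Second, circulating antibody drug can hide ADA in some assays. If this assay is of that kind, a negative taken with MOR00208 on board is uninformative, and the table would still report it as *no*. The paired concentration that could separate the two cases is scheduled at every ADA visit and is not used. Protocol 15.13.1 reports that MOR00208 interfered with CD19 detection in the phase I trial and made those data hard to interpret. That is a different assay, but it shows that drug interference is a known problem in this programme.

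There is also a gap in the categories. A patient with no baseline sample fits none of them once a later result exists, because *yes* and *no* both require a negative baseline.

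At stake is the reading of a low figure, for example 0 of 12, for a named secondary objective.

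**Working it through.** The plan states no ADA rate, sample size or power, so there is no figure of that kind to reproduce. The dose calendar can be checked: infusions on study days 1, 4, 8, 15, 22, 29, 36, 43 and 50 make C3D1 (day 57) the tenth, which agrees with SAP 4.9.2.

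**Drug on board.** Inputs: the dosing schedule (Protocol 8.1.1) and Protocol 4.5.2, "MOR00208 showed a terminal elimination half-life of approximately 14 days". One-compartment superposition, in units of the level added by one dose:

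level(t) = sum over earlier doses d of 2^(−(t − d)/14)

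- C2D1 (day 29): intervals of 28, 25, 21, 14 and 7 days give 0.25 + 0.29 + 0.35 + 0.50 + 0.71 = 2.10.
- C3D1: 0.25 × 2.10 + (0.25 + 0.35 + 0.50 + 0.71) = 2.34.
- C5D1 1.35; C7D1 1.02; C9D1 0.38; C11D1 0.34.
- Monthly troughs from C13D1: 0.25/(1 − 0.25) = 0.33.
- EOT 30 days after the last monthly dose: 2^(−30/14)/(1 − 0.25) = 0.226/0.75 = 0.30. Half-lives of 7 and 21 days give 0.05 and 0.62.

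Post-baseline ADA samples: C2D1, C3D1, ten odd cycles from 5 to 23, and EOT, which makes 13. With full dosing, drug is expected in all of them. A patient who stops MOR00208 well before the partner drug is an exception.

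In these units, an assay tolerance above 2.34 alters no result. One below 0.30 makes every negative in this schedule inconclusive.

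**Boosted responses.** N = 12 (SAP 3.10), so one patient is 1/12 = 8.3 points. Illustration with one *yes* and two baseline-positive patients:

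| Boosted among the two | Item 3 *yes*/12 | Induced + boosted/12 |
|---|---|---|
| 0 | 8.3% | 8.3% |
| 1 | 8.3% | 16.7% |
| 2 | 8.3% | 25.0% |

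If *not evaluable* patients leave the denominator, the item 3 figure becomes 1/10 = 10.0%.

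**Masking.** Assume a true incidence of 10% and detection of half the cases. The expected observed rate is 5%, and the chance of seeing 0/12 rises from 0.90^12 = 28% to 0.95^12 = 54%. Both inputs are assumptions.

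**The case against.** Much can be said for the plan.

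- **Baseline-positive patients are not lost.** They stay in the Immunogenicity Analysis Set (SAP 3.6.5), count as positive at each positive visit (item 2), enter the titer summary (item 4), and appear in the listing: "The results of the anti-MOR00208 antibody assessment will be listed for each anti-MOR00208 sample analyzed". A reader might infer that they are dropped from reporting. The documents do not support that. The gap is confined to the count of patients who develop ADA, and with about 12 patients a titer rise would be visible in the listing.
- **Masking is not shown.** The model shows that drug is present, not that any negative is wrong. Its unit is not a concentration that can be set against an assay limit, and it ignores any distribution phase.
- **The direction is not fixed.** A reader might infer that incidence can only be understated. That does not follow. A tolerant assay gives no bias. The item 3 denominator is unstated, and removing *not evaluable* patients can raise the percentage. One positive sample is enough for *yes*. With an assumed confirmed false-positive rate of 0.5% per sample, 1 − 0.995^13 = 6.3% of truly negative patients would be called positive. A true 5% detected half the time would then read 0.025 + 0.975 × 0.063, or about 8.7%, an overstatement.
- **The missing-baseline gap has no direction of its own.** Unscheduled values before C1D1 can serve as baseline (SAP 4.1.4), and other critical missing data go to documented data review (SAP 4.14.1).
- **The analysis is descriptive.** 0/12 has an exact 95% upper limit of 26.5%, so it could not establish absence of immunogenicity. SAP 1 allows labelled post-hoc analyses.

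All of this stands. It limits the claim but does not answer it: the headline table would still place a boosted patient outside the count and show an uninformative negative as *no*. A rule set before database lock is also worth more than a post-hoc merge.

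**Conclusion.** As written, item 3 cannot register a boosted response and cannot separate a true negative from a possibly masked one. Treatment-emergent ADA may therefore be understated, on either of two conditions: that some baseline-positive patients are boosted, or that the assay is sensitive to MOR00208 at the levels present. Neither can be judged from the documents, which give no drug tolerance and no expected frequency of baseline positivity. The 8.3 points per patient apply only to a patient who is actually boosted, or who lacks a baseline sample and is later positive. Other baseline-positive or baseline-missing patients leave the count unchanged. Calling masked negatives inconclusive adds no positive patients; it changes what *no* means. The primary safety endpoint is not touched. This is a cheap improvement to a secondary endpoint table, and it goes beyond missing detail because the stated rule itself produces the misclassification.

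**What to change.** Amend SAP 4.9.1 item 3, using data already scheduled:

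1. **Boosting.** Replace *not evaluable* for baseline-positive patients with *treatment-boosted* or *not boosted*. Fix the required titer rise before database lock and justify it by the precision of the titer assay. Report induced, boosted and total treatment-emergent ADA over a stated denominator.
2. **Drug on board.** Cite the assay's validated drug-tolerance limit. Report a negative post-baseline sample as *inconclusive* when the paired MOR00208 concentration exceeds that limit. *No* then needs at least one conclusive negative post-baseline sample and no positive one.
3. **Missing baseline.** Assign these patients to *positive, baseline unknown* or *negative, baseline unknown*.

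The cost is SAP wording, a merge of the ADA and concentration data, and obtaining the tolerance limit from the assay validation. No new samples are needed. The downside is that some patients move from *no* to *inconclusive*. With a low-tolerance assay that could be most of them, because no ADA sample is planned after washout. If the assay is tolerant, the table does not change and its negatives become credible.

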4.9.2 Pharmacokinetic Analysis

Individual plasma samples for the analysis of MOR00208 PK will be collected on various study days. For evaluation of PK metrics, patients will be considered who have at least one quantifiable MOR00208 serum concentration (the PK analysis set, PKAS).

Bioanalytical Assessment of Pharmacokinetic Serum Samples

MOR00208 concentration values for each serum sample are to be determined using a validated Ligand Binding Assay. A separate bioanalytical phase plan and report will be generated that provide details on samples handling and processing, methods used for sample analysis, statements on quality control/quality assurance (QC/QA) and results of the each individual sample analyzed for each patient by the bioanalytical labs.

Data Analysis

MOR00208 serum concentrations will be summarized based on nominal (scheduled) sampling times. Serum concentrations below the limit of quantification or missing data will be labelled as such in the concentration data listings. Analyte concentrations that are below the limit of quantification (BLQ) will be assigned a value of zero when they precede the first quantifiable sample. All other BLQ samples will be treated as missing data. Summary statistics for MOR00208 serum concentrations will include n, arithmetic mean, standard deviation, geometric mean, coefficient of variation (CV), median, minimum and maximum. The CV will be expressed as a percentage and calculated as follows:

- $CV \text{ of the arithmetic mean (\%)} = \text{standard deviation}/\text{mean} * 100$
- $CV \text{ of the geometric mean (\%)} = \sqrt{\text{exp}(\text{variance for log transformed data}) - 1} * 100$.

Concentration figures (linear and log y-axis) of mean concentrations \pm standard deviation (StD) will be presented. Individual MOR00208 serum concentrations may be excluded from summary statistics and concentration figures (mean) if the actual collection time/date of the sample exceeds allowable windows relative to the scheduled collection time/date.

- For samples collected 1h after the end of MOR00208 infusion, results will be excluded from summary statistics if the deviation of the actual collection time is larger than ± 15 min from the scheduled collection time.
- Results of PK samples collected outside of the allowed window (in days) relative to the scheduled collection day will be excluded from summary statistics. Each 28 day cycle will be considered separately.

Irrespective of exclusion of data points from summary statistics, each obtained MOR00208 serum concentration will be listed and reported.

Accumulation of MOR00208 will be investigated by comparing the average concentration of pre-dose and the average concentration 1 hour post-dose of Cycle 3 Day 1 (i.e. the 10th dose) with the

corresponding mean from the previous visit for which MOR00208 concentration data is available using analysis of variance (ANOVA) ($\alpha = 0.05$). If no significant difference is found, Cycle 3 Day 1 will be compared to previous visit for which MOR00208 concentration data is available and so forth until two consecutive times a significant difference is found.

Furthermore, additional PK sample assessment may be performed to determine bioactive MOR00208 serum concentrations. These MOR00208 serum concentrations will only be reported in listings and none of the above described PK analyses (tables, figures) will be performed using these bioactive MOR00208 serum concentrations.

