8.6 Dose Modifications of MOR00208

In a phase I study of MOR00208 in CLL, the MTD was not reached and the drug was generally well tolerated, IRRs of grade 1 or 2 being the most common toxicities. Treatment-related grade 3 or 4 AEs occurred in 5 out of 27 patients and included neutropenia, thrombocytopenia, increased AST, febrile neutropenia, and TLS. There was one CLL patient with dose-limiting toxicity (DLT) of grade 4 neutropenia lasting ≥ 7 days with febrile neutropenia

Dose reductions of MOR00208 are not allowed during the course of the study due to the relatively mild AE profiles of MOR00208.

In the case of clinically significant grade ≥ 3 toxicities that are not described in Table 8 & Table 9 and Sections 8.9 & 8.10:

- MOR00208 doses should be omitted until the toxicity grading diminishes in severity to grade ≤ 1 or returns to a baseline grade, provided the condition was pre-existing at baseline
- Missed doses of MOR00208 should not be made up for. If the patient misses a subsequent MOR00208 dose, the second missed dose should be administered immediately after the toxicity resolves.
- During monthly treatment with MOR00208, every missed dose should be administered immediately after the toxicity resolves.

If the Investigator considers a clinical finding and/or laboratory parameter change to represent natural fluctuation or progression of the underlying disease, then it will be at the Investigator's discretion (and depend on the assessment of the individual risk/benefit ratio) to determine whether the patient should be dosed. The decision and rationale behind the decision should be documented in the source data.

For MOR00208 dose modification instructions for specific toxicities, see Table 8 & Table 9 and Sections 8.9 & 8.10.

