4.1.5 Exclusion of Data from the Statistical Analysis

No data will be excluded from the analyses, including any outliers.

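### MOR00208 concentrations are averaged by nominal time and screened only on collection minute and day, never on dosing history, and the end-of-treatment mean has no defined time since last dose

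*SAP*

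**What the plan says.** SAP 4.9.2 sets the basis of the summaries: "MOR00208 serum concentrations will be summarized based on nominal (scheduled) sampling times". The lead sentence on exclusions is permissive: "Individual MOR00208 serum concentrations may be excluded from summary statistics and concentration figures (mean"). The two bullets under it are mandatory. For the 1-hour post-dose sample, "results will be excluded from summary statistics if the deviation of the actual collection time is larger than ± 15 min from the scheduled collection time". For days, "Results of PK samples collected outside of the allowed window (in days) relative to the scheduled collection day will be excluded from summary statistics". All values are still listed.

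Elsewhere the SAP says the opposite. Section 4.1.5 states "No data will be excluded from the analyses, including any outliers", and 4.14.2 repeats it.

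No dosing-history condition appears in 4.9.2, in the PK analysis set (SAP 3.6.4: one dose and one quantifiable value) or in Protocol 12.8. Yet omissions are foreseen. Under Protocol 8.6, for clinically significant toxicity of grade 3 or above not covered by the specific tables, "MOR00208 doses should be omitted until the toxicity grading diminishes in severity to grade ≤ 1" or baseline. A missed dose is generally not made up, except in the monthly phase, where 8.6 and 8.11 provide for make-up. Protocol 8.12 and SAP 4.7.4 also tolerate some missed doses.

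The schedule of assessments (Protocol Table 10, SAP Table 2) includes a PK sample at the end-of-treatment visit. That visit is tied only loosely to the last dose, preferably no more than 30 days after it.

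**The concern.** With a half-life of about two weeks, a MOR00208 concentration depends much more on which infusions were given than on small shifts in sampling time. The SAP screens the second and ignores the first. A by-visit mean can therefore mix patients on the planned schedule with patients who skipped or delayed an infusion, with nothing to mark them.

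The PK profile is a secondary objective with about 12 patients per cohort. Toxicity is one cause of omission, and the MOR00208 hold rules differ between cohorts (Protocol Tables 8 and 9), so the mixture could differ between cohorts too. The Cycle 3 Day 1 accumulation comparison in 4.9.2 has no dosing-history condition either, and the SAP does not say whether the exclusions apply to it.

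The end-of-treatment sample is a sharper case. It has one visit label but no single time since dose and no single preceding schedule.

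**Working it through.** **Inputs from the documents.** Half-life: "MOR00208 showed a terminal elimination half-life of approximately 14 days" (Protocol 4.5.2). Schedule: Days 1, 4, 8, 15 and 22 of Cycle 1, weekly in Cycles 2-3, Days 1 and 15 in Cycles 4-6, then Day 1 of each cycle. PK samples: pre-dose and 1 hour after infusion at C1D1, C1D4, C1D15, C2D1, C2D15, C3D1 and C3D15; pre-dose only in odd cycles from Cycle 5.

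**Assumptions.** One compartment, linear, equal unit bolus doses, no target-mediated clearance. Half-life sensitivity range 10-21 days (assumed).

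**Check on the schedule.** Doses up to C3D1: 5 + 4 + 1 = 10, matching the SAP's statement that C3D1 is the 10th dose. The documents give no figure for the effect of an omission.

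**Formula.** k = ln 2 / 14 = 0.0495 per day. Pre-dose level = sum of exp(-k × days since each earlier dose). The 1-hour post-dose level adds one unit. The infusion just before the sample is removed and the result compared with the full schedule.

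| Sample | Full | Last dose omitted | Pre-dose shortfall | 1-hour post-dose shortfall |
|---|---|---|---|---|
| C1D15 | 1.787 | 1.080 | 39.6% | 25.4% |
| C2D1 | 2.101 | 1.394 | 33.7% | 22.8% |
| C2D15 | 2.257 | 1.550 | 31.3% | 21.7% |
| C3D1 | 2.336 | 1.629 | 30.3% | 21.2% |
| C3D15 | 2.375 | 1.668 | 29.8% | 21.0% |
| C5D1 | 1.349 | 0.849 | 37.1% | not sampled |
| C7D1 | 1.022 | 0.522 | 48.9% | not sampled |

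C3D1, for example: pre-dose 1 - 1.629/2.336 = 30.3%; post-dose (2.336 - 1.629)/3.336 = 21.2%. C1D4 is left out because an omitted C1D1 leaves no earlier dose.

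**Half-life sensitivity (21 to 10 days).** C3D1 pre-dose 23% to 39%; C7D1 35% to 62%.

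**Monthly phase.** At C9D1 the full-schedule level is 0.376. If C8D1 is given 7 days late the level is 0.480, or +27.5%; 14 days late gives 0.626, or +66%. Only if C8D1 is never given does it fall to 0.126, or -66%.

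**Effect on a visit mean, one affected patient of 12.** Shortfall divided by 12: C3D1 30.3/12 = 2.5%; C7D1 48.9/12 = 4.1%; C9D1 66.4/12 = 5.5% (dose never made up). For C8D1 made up 7 days late, the C9D1 mean rises by 27.5/12 = 2.3%.

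**Timing deviations, 1 - exp(-k × delay).** 20 minutes 0.07%; 1 day 4.8%; 2 days 9.4%; 3 days 13.8%. The 20-minute figure counts elimination only.

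**End of treatment.** Seven days after C3D22: 2.39. Thirty days after C9D1: 0.31. Ratio 2.39/0.31 = 7.7.

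**The case against.** The strongest objection is that a sample after an omitted infusion is not wrong. It is the exposure the patient had, and removing it restricts the summary to patients who tolerated dosing. This stands: observed exposure is a legitimate target and should remain the main summary. What is missing is a way to tell it apart from exposure on schedule.

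Second, the effect on a mean is a few percent per affected patient, the documents give no omission rate, medians and geometric means are also planned, and every value is listed. This also stands and limits the weight of the point. It does not help with the end-of-treatment mean.

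Third, a reader might infer that the rule retains troughs up to 66% too low and so pulls means down. The documents do not support that as a general statement. The 66% needs a monthly infusion missed and never given, whereas Protocol 8.6 and 8.11 provide for make-up; a late make-up pushes the next trough up.

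Fourth, a reader might infer that the windows throw away nearly correct samples. That is fair for post-infusion samples some minutes beyond the limit, if distribution is ignored. It is weak for days. The windows are ±1 day through Cycle 3 and ±2 days afterwards, so one-day shifts are normally kept. On whole days, exclusion normally starts at 2 days (9.4%) or 3 days (13.8%). Only C1D4, with no printed tolerance, might lose a one-day shift. The 15-minute limit is already looser than the protocol's 10-minute sampling tolerance.

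Finally, checking only the last infusion would not suffice. Omitting C2D15 but giving C2D22 still leaves C3D1 low by 0.5/2.336 = 21%.

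**Conclusion.** The structural point holds: nothing in the SAP's PK rules looks at dosing history. The size is moderate and the direction not fixed. Under the model above, samples after one omitted infusion in Cycles 1-6 are about 30-49% low pre-dose, and about 21-25% low at 1 hour post-dose in Cycles 1-3. In the monthly phase a late make-up biases the next trough upward. One affected patient of 12 shifts a visit mean by roughly 2.5-5.5%, the upper end needing an infusion that is never made up. A cohort difference is plausible but cannot be quantified from the documents.

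The nominal-time end-of-treatment mean is not interpretable whatever the omission rate; 7.7-fold is the spread between two extreme cases, not a typical one. The conflict between 4.9.2 and the two no-exclusion statements is plain from the text.

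These are descriptive summaries of a secondary endpoint and, possibly, the accumulation comparison. The change should be made, but no safety conclusion depends on it.

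**What to change.** Amend SAP 4.9.2:

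1. Keep the planned observed-exposure summary. Flag each sample by dosing history: any omitted, incomplete or made-up infusion within a stated look-back, or an actual interval since the last infusion more than 2 days off schedule. Add a by-visit sensitivity summary without flagged samples, and apply it to the C3D1 accumulation comparison as well.
2. Report end-of-treatment concentrations individually against actual days since the last infusion and the last schedule (weekly, biweekly or monthly), not as a nominal-time mean.
3. Choose between *may* and *will* for the timing exclusions, and state 4.9.2 as an explicit exception to 4.1.5 and 4.14.2.

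The cost is SAP wording and programming. MOR00208 administrations are already recorded in the eCRF (Protocol 8.12), and the existing rule already relies on actual sample times. The downside is one extra table or figure and a smaller n in the sensitivity summary. No change to dosing or make-up rules is proposed.

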3.10 Sample Size

The primary endpoint of this study is the incidence and severity of AEs in Cohort A (MOR00208 combined with idelalisib) and Cohort B (MOR00208 combined with venetoclax) and will be analyzed

descriptively. In each cohort approximately 12 patients will be enrolled. No formal sample size calculation was performed and no formal statistical hypothesis testing is planned.

4 Statistical Methodology

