4.1.2 Statistical Significance

No formal statistical hypothesis testing is planned.

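### The MOR00208 accumulation analysis lets a non-significant ANOVA stand for no difference, so the levelling-off may be dated too early

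*SAP*

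**What the plan says.** SAP 4.9.2 takes the mean pre-dose and mean 1-hour post-dose levels at C3D1, the tenth dose, and tests each against its counterpart at the nearest earlier visit that has PK data, using ANOVA at alpha 0.05. The step rule is: "If no significant difference is found, Cycle 3 Day 1 will be compared to previous visit". The chain ends under a separate condition, worded as "and so forth until two consecutive times a significant difference is found". The section states no patient term, measurement scale, ratio, interval or margin, and does not say whether the cohorts are pooled. It never speaks of a plateau or steady state, and does not say how a non-significant step will be reported.

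Three other places bear on this:

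- SAP 3.1, Table 1, describes the PK endpoint as concentration-time profiles and "appropriate individual PK parameters (e.g., accumulation ratios"). Section 4.9.2 gives no derivation for such ratios. Appendix F lists a concentration summary (Table 14.4.1) and the accumulation test (Table 14.4.2), but no output of ratios.
- SAP 4.1.2 says: "No formal statistical hypothesis testing is planned". Protocol 12.8 plans non-compartmental parameters with descriptive statistics and leaves details to the SAP. SAP 4.17 does not list the ANOVA as a change.
- SAP 3.10 says: "In each cohort approximately 12 patients will be enrolled". On the basis for that number it adds: "No formal sample size calculation was performed".

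The schedule (SAP Table 2) has pre-dose and 1-hour post-dose PK samples at C1D1, C1D4, C1D15, C2D1, C2D15, C3D1 and C3D15.

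**The concern.** Significance is the only criterion in the chain, so whether two visits count as different depends on the power of each step. Nothing in the plan establishes that power. Failing to reject with a dozen patients does not show that concentrations have stopped rising.

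The missing patient term makes this worse. The same patients contribute at every visit, so differences between patients cancel from the visit-to-visit contrast. An ANOVA that ignores this still puts the between-patient variance into its error term, and the test becomes far stricter than its nominal 5%.

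The PK profile is a secondary objective. Protocol 5.7 links efficacy to exposure over the first two cycles, which is the stretch in which the chain has to separate visits. The C3D15 sample, which could show whether levels are still rising after C3D1, plays no part in the chain.

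**Working it through.** The documents give no power, CV or accumulation threshold for this analysis, so there is no planned figure to reproduce. The one checkable count is right: five doses in Cycle 1 and four in Cycle 2 make C3D1 the tenth dose.

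**Inputs.** The half-life is about 14 days (Protocol 4.5.2). Equal doses fall on days 0, 3, 7, 14, 21, 28, 35, 42, 49 and 56 (C3D1 = day 56). There are 12 patients. Between-patient CV 30–50% and within-patient CV 15–25% are assumptions.

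**Step 1, expected troughs.** One-compartment superposition, in units of one dose: trough(t) = sum over earlier doses of exp(−k(t − dose day)), with k = ln 2/14. For C1D15 (day 14): 0.500 + 0.580 + 0.707 = 1.787.

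| Pre-dose visit | Trough | C3D1 ÷ visit |
|---|---|---|
| C1D4 | 0.862 | 2.71 |
| C1D15 | 1.787 | 1.31 |
| C2D1 | 2.101 | 1.11 |
| C2D15 | 2.258 | 1.035 |
| C3D1 | 2.336 | 1 |
| C3D15 | 2.375 | – |

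**Step 2, why the patient term matters.** The log-scale variance for a given CV is ln(1 + CV²). CVs of 30%, 50%, 15% and 25% give 0.0862, 0.2231, 0.0223 and 0.0606. The target is ln(1.307) = 0.268.

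- With no patient term, the test needs an observed log difference above t(22 df) × √(2 × total variance/12). At CVs 30%/15% (between/within): 2.074 × √(2 × 0.1085/12) = 0.279, a rise of 32%. At 50%/25%: 2.074 × √(2 × 0.2837/12) = 0.451, a rise of 57%. The expected 31% falls short of both.
- Paired on logs, the standard error is √(2 × within variance/12): 0.061 at within-patient CV 15% and 0.101 at 25%. The target is then about 4.4 and 2.7 standard errors.

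**Step 3, power for the 31% rise** (two-sided 0.05, 20,000 simulated trials per row; repeat runs differ by about one percentage point):

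| Between / within CV | No patient term, raw scale | Paired, raw scale | Paired, log scale |
|---|---|---|---|
| 30% / 15% | 45% | 97% | 98% |
| 30% / 25% | 31% | 64% | 68% |
| 50% / 15% | 8% | 94% | 98% |
| 50% / 25% | 8% | 58% | 68% |

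With no true difference, the test without a patient term rejects in 0–0.5% of trials. For the 11% rise from C2D1, power is 0.1–3% without a patient term and 16–36% paired on logs.

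**Step 4, overall accumulation.** The 2.71-fold contrast with C1D4 is significant in at least 99% of runs, even with no patient term.

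**Step 5, post-dose samples.** Adding one dose unit to each trough gives C3D1 ÷ C1D15 = 3.336/2.787 = 1.20. This is a smaller contrast, so it is harder to detect than the pre-dose one.

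**The case against.** A reader might infer that real accumulation of about 30% would usually be reported as no accumulation at all. The documents do not support that. A non-significant step does not end the analysis; it sends C3D1 back to an earlier visit, and by C1D4 the contrast is large enough to be found almost every time.

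The word usually is not secure either. The SAP says only ANOVA, and a repeated-measures form also fits the wording. With a patient term on the raw scale, the 31% rise is found in 58–97% of trials under the same CVs. Pooling the cohorts would also help. Treating visits as independent samples, a ratio of 1.30 with 24 patients and no patient term is found in 86%, 64% and 47% of trials at CV 30%, 40% and 50%. With 12 patients the figures are 55%, 36% and 26%.

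Three further points are fair:

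- Reading a non-significant step as a plateau is an inference from the rule, not a statement in the SAP.
- Section 4.9.2 already gives arithmetic and geometric means by nominal time, figures, and a listing of every concentration, including C3D15. Ratios of geometric means could be read from these, though without within-patient intervals. Accumulation ratios appear in Table 1 only as an example, and SAP 3.6.4 makes PK parameters depend on the data.
- The protocol synopsis allows P values for specific variables alongside its statement on hypothesis testing, and SAP 4.21 sets their format. The clash with SAP 4.1.2 is therefore one of drafting.

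What stands is that power runs from poor to good depending on a modelling choice the SAP leaves open, and that no reading of ANOVA makes non-significance evidence that levels have stopped rising.

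**Conclusion.** The concern holds in limited form. The chain rests on significance alone and can date the levelling-off of MOR00208 too early. If no patient term is used, the modelled 31% pre-dose rise from C1D15 to C3D1 is missed in about 54–92% of trials, against about 2–32% for a within-patient log-scale comparison. Both figures rest on 12 patients, the assumed CVs, a one-compartment model and an approximate half-life from the phase I study. That non-significance is not evidence of equality depends on none of these.

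The absence of any derivation for accumulation ratios is a smaller but certain gap. The listings, the descriptive PK summaries and the primary safety endpoint are unaffected, and the SAP ties no trial decision to this step. It should be changed, but it does not threaten the trial's main conclusions.

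**What to change.** In SAP 4.9.2, replace the ANOVA chain with a mixed model on log concentration, with visit as a fixed and patient as a random effect, fitted separately to pre-dose and 1-hour post-dose samples. Omit the C1D1 pre-dose values, which the SAP sets to zero when below quantification and which have no logarithm. State whether the cohorts are modelled separately or together.

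Report geometric mean ratios of C3D1 and of C3D15 to each earlier visit with 90% confidence intervals, plus individual accumulation ratios, and add these to Appendix F. State that a plateau will not be inferred from a non-significant result. A margin within which the interval must lie before a plateau is declared is optional; if used, it should be fixed before the data are seen. Estimates with intervals also remove the tension with SAP 4.1.2, and SAP 4.17 can record the change.

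The cost is SAP wording and one short program. No new samples or data are needed.
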